4.3.2 Medication Check Visits vs. Research Visits

In a pragmatic trial, research assessments/interactions that could impact outcomes and, thus, reduce the generalizability of the results to real world practice are minimized. However, this goal must be balanced with the need to closely monitor safety given that CTN-0080 is the first trial to evaluate the BUP-XR formulation in pregnant women. This balance will be achieved by including weekly Medication Check Visits, which include a minimal number of assessments and procedures (see **Table 3**), while limiting more intensive data collection to Research Visits, which will occur less frequently (e.g., monthly during pregnancy, etc.; see **Table 3**).

4.3.3 Non-inferiority Primary Analysis

As detailed in the conceptual model (**section 4.4**), BUP-XR may improve outcomes, relative to BUP-SL, due to its superior PK profile. However, to be consistent with the design of the CAM2038 Phase 3 trial,⁵⁹ CTN-0080 will utilize a non-inferiority design. A finding of non-inferiority would suggest that BUP-XR is a reasonable alternative to BUP-SL, thus expanding available treatment options. This is important because, at present, the number of BUP providers is insufficient to meet treatment needs (particularly in rural areas). A significant concern of clinicians who are unwilling to prescribe BUP-SL is the potential for diversion;³⁸ removal of this barrier would, thus, have the potential to increase the availability of treatment.

4.3.4 Standardization of NOWS Scoring and Treatment

The primary outcome measure for CTN-0080 is illicit opioid use during pregnancy. This, combined with the goal of utilizing pragmatic features where feasible, suggests that standardization of NOWS scoring/treatment at the delivery hospitals, which are not participating in the trial as study sites, should not be undertaken. However, the variability in delivery-hospital approach to NOWS could adversely impact the evaluation of treatment effects on NOWS severity, which is a key secondary measure. Hence, it was decided to decrease delivery-hospital variability. Based on a review of the literature, as well as consensus of the NOWS experts of the protocol development team, it was determined that participants are only eligible (see **section 6.4.2**) if they plan to deliver at a hospital that meets all the following requirements:

- 1) has a written protocol for the management of NAS/NOWS since it has been shown that implementation of a standard protocol decreases length of opioid treatment days, infant LOS, and use of adjunctive drug therapy.^{60, 61} Based on a survey of Better Outcomes Through Research for Newborns (BORN) hospitals,⁶² it is estimated that 88% of potential delivery hospitals will have a written protocol for NAS/NOWS management.
- 2) offers rooming-in while infants are being observed for NAS/NOWS, since rooming-in is associated with decreased need for pharmacologic treatment for NAS/NOWS and shorter LOS.⁶³ Based on the results of the BORN survey,⁶² it is estimated that 73% of potential delivery hospitals will offer rooming-in.
- 3) does not send infants home on opioids for the treatment of NAS/NOWS. This is required since infant NOWS severity will be measured by total number of opioid treatment days as assessed by medical record; opioids provided at home would not be captured making the outcome inaccurate. Based on the results of the BORN survey,⁶² it is estimated that 83% of potential delivery hospitals will not send infants home on opioids.

[figure not shown]
In addition, participants are only eligible to participate (see **section 6.4.2**) if they plan to deliver at a hospital that has provided information about their approach to NAS/NOWS, so that important variables can be controlled for in the NOWS analyses (see **section 7.4.2**).

4.3.5 Potential Ancillary Studies

CTN-0080 has the potential to serve as a parent trial for ancillary studies that could make further important contributions to the field. It is likely that ancillary studies will be conducted at a subset of sites due to the need 1) for specific expertise and/or equipment that may not be available at all locations and 2) to avoid overwhelming potential CTN-0080 participants with study requests. An example of the former would be a study of brain development requiring pediatric neuroimaging. Another example of an ancillary study, the pursuit of which will be encouraged by interested investigators, would be a lactation sub-study to assess the exposure of the infants to buprenorphine and/or buprenorphine-naloxone through breastfeeding. There are a limited number of lactation studies with women maintained on BUP-SL,⁶⁴⁻⁶⁷ with the largest study including 10 women.⁶⁷ To date, there are no published lactation studies for breastfeeding women maintained on BUP/NX-SL. Thus, even a relatively small lactation sub-study could contribute valuable information to the field.

4.4 Conceptual Model

A secondary objective of MOMs is to test a conceptual model of the mechanisms by which BUP-XR may improve mother and infant outcomes relative to BUP-SL; the conceptual models to be tested are outlined in **Figures 2a** (mother outcomes) and **2b** (infant outcomes).

[figure not shown]
4.4.1 Mother Outcomes

The conceptual model describing the mechanism by which BUP-XR may improve mother outcomes relative to BUP-SL is outlined in **Figure 2a**. As noted above, BUP plasma concentrations ≥ 1 ng/mL should be sufficient for suppressing opioid withdrawal²⁷ and, for the subset of participants using illicit opioids, BUP plasma concentrations ≥ 1.25 ng/mL should be sufficient to block the illicit opioid effect.³⁰ The main conceptual model will focus on the ≥ 1 ng/mL threshold since this should apply to all of the participants whereas the ≥ 1.25 ng/mL threshold is

pertinent for participants using illicit opioids; the ≥ 1.25 ng/mL threshold will be evaluated in exploratory analyses. There is evidence that pregnant women may have BUP plasma concentrations < 1 ng/mL for most of their dosing interval.³¹ It has been hypothesized that inadequate BUP plasma concentrations may account for illicit opioid use and treatment dropout in pregnant women treated with BUP-SL.²⁶ For participants who consent to the CMA sub-study, trough BUP plasma levels (C_{\min}) will be assessed in conjunction with the study week 3 and 5 visits. Based on the half-life of BUP-XR,²⁹ it is estimated that steady state will be reached at approximately study days 20-25; thus, steady state should be reached by study week 5. The rationale for including the week 3 sample is that, in order to predict treatment dropout, data need to be obtained from participants who subsequently dropout and research suggests that BUP dropout tends to occur within the first 30 days of treatment.^{2, 16} Based on its PK profile, BUP-XR, relative to daily BUP-SL, should result in a greater proportion of women with $C_{\min} \geq 1$ ng/mL, which, in turn, is hypothesized to result in less illicit opioid use and better BUP medication adherence. However, the difference in C_{\min} between the BUP-XR and BUP-SL groups should be less pronounced in women following a split dosing schedule (i.e., taking BUP-SL more than once a day) or a higher dose; thus, BUP-SL dosing frequency and dose will be used to define BUP-SL subgroups. Three covariates that are likely to impact mother outcomes will be controlled for in the analyses: 1) study site (e.g., due to the provision of different psychosocial services, etc.); 2) use of other substances; and 3) route of administration of illicit opioid use (intravenous vs. not intravenous). It is important to note that C_{\min} is being measured to test a conceptual model; there is insufficient evidence to support its use in guiding BUP dosing decisions and the results will not be given to the treating provider.

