Adherence to BUP treatment during pregnancy through 12 months postpartum is a clinically important outcome due to the heightened vulnerability to relapse¹³ and overdose²² during this period. Adherence to BUP treatment during pregnancy will be scored as the number of days of adherence divided by the number of days between randomization and delivery. Postpartum adherence to BUP treatment will be scored as the number of days of adherence post-hospital-discharge divided by the number of post-hospital-discharge days in the 12-month postpartum phase. Adherence to BUP-XR will be based on study records (i.e., BUP-XR Injection documentation). For BUP-XR, the receipt of a weekly injection will be scored as 7 days of adherence. If a particular day is covered by two injection windows (e.g., injections on study day 7 and study day 13, where study day 6 overlaps the two seven-day windows), the adherent day will only be counted once. For monthly injections, a participant will be considered as adherent for 28 days and overlapping intervals are handled similarly as for the weekly injections. Adherence to BUP-SL will be defined as: 1) study records showing that BUP-SL was dispensed to the participant (i.e., BUP-SL Dispensing documentation); 2) self-reported adherence will be assessed at the weekly Medication Check Visits; and 3) UDSs positive for buprenorphine/norbuprenorphine. In cases where participants discontinue study medication to transfer to an alternative treatment (e.g., methadone, extended-release naltrexone), a score of 0 days of adherence will be given for the time period post discontinuation. The rationale for not “crediting” receipt of methadone or extended-release naltrexone as adherence is that a switch to an alternative medication is an indicator that BUP-XR / BUP-SL was, in some way, ineffective for the participant and the score of 0 is consistent with the lack of effectiveness. In cases where participants discontinue study medication to transfer to BUP from an alternative provider or were provided non-study BUP during hospital stays or incarceration, a release of information will be obtained, and adherence will be based on clinic/pharmacy records (BUP-XR) or, for BUP-SL, on clinic/pharmacy records along with participant self-report and study UDSs if available. For the case where clinic/pharmacy records could not be obtained for any reason, the participant will be considered non-adherent. If participants drop out of the study prematurely, they will be considered non-adherent for all days after drop-out. In the case of intermittent missing UDSs (e.g., UDSs not collected for any reason but the participant did not drop out), then adherence will be based on study/clinic/pharmacy records and self-report.

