
10.3.2 Key Outcomes

Illicit opioid abstinence during pregnancy. As noted previously, this primary outcome measure is based on urine testing. It is operationalized as the percent of expected UDSs that are negative for illicit opioids. One UDS is expected at the time of each weekly Medication Check Visit between randomization and delivery – any missing UDS is imputed as positive (see **section 10.3.5**). The number of expected UDSs will be dependent on the length of time between randomization and

delivery, thus we operationalize this primary outcome measure as the *percent* of expected UDSs that are illicit opioid-negative.

The non-inferiority design results in the following hypotheses where μ_A is the mean in arm A and Δ the non-inferiority margin:

$$H_0(BUP - XR \text{ is inferior to BUP - SL}): \mu_{XR} - \mu_{SL} \leq -\Delta$$

$$H_1(BUP - XR \text{ is non - inferior to BUP - SL}): \mu_{XR} - \mu_{SL} > -\Delta .$$

To evaluate non-inferiority at the 2.5% significance level, the two-sided 95% confidence interval for the treatment effect, $\mu_{XR} - \mu_{SL}$, will be calculated using a mixed effects model where treatment arm is a fixed effect and the three randomization factors (site, EGA and BUP-SL status at randomization) are random effects. If the lower limit of the confidence interval is greater than -0.15 (i.e., $\Delta=0.15$), we will reject the null hypothesis and conclude non-inferiority of BUP-XR to BUP-SL. Only if the null hypothesis is rejected will superiority of BUP-XR to BUP-SL be considered. This will involve examining the two-sided 95% confidence interval for the treatment effect, $\mu_{XR} - \mu_{SL}$. If the lower limit is above zero, then we can conclude that the extended-release formulation is superior to the sublingual formulation. If this order of testing is followed, then there is no need to adjust for multiplicity.^{176, 181} Additional covariates for secondary modeling are described in **section 7.4**. In the event that the distributional assumptions involved in the mixed effects model are not met, which is likely, alternative non-parametric methods will be considered for this modelling such as quantile regression.

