10.8 Conceptual Model Analyses

Structural equation modeling¹⁸⁶ will be used to test the conceptual models described in **section 4.4**.

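### The mother conceptual model places trough buprenorphine at weeks 3 and 5 ahead of pregnancy outcomes scored from randomization, with no lag or adjustment for behaviour before the sample

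*Combined protocol and SAP*

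**What the plan says.** Section 4.4.1 sets out a directed path. BUP-XR should put more women at C_min of at least 1 ng/mL, and this in turn "is hypothesized to result in less illicit opioid use and better BUP medication adherence". The troughs "will be assessed in conjunction with the study week 3 and 5 visits". The 1 ng/mL threshold is the main model; 1.25 ng/mL is exploratory.

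The pregnancy outcomes on the right of that path are defined elsewhere:

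- Adherence (7.2.1.1) is "scored as the number of days of adherence divided by the number of days between randomization and delivery".
- Illicit opioid use (10.3.2) is the percentage of expected urines that are negative: "One UDS is expected at the time of each weekly Medication Check Visit between randomization and delivery".

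Section 7.2.1.1 also has a postpartum score: "Postpartum adherence to BUP treatment will be scored as the number of days of adherence post-hospital-discharge". Postpartum illicit use has its own definition in 7.1.2.2.

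On analysis, section 10.8 says only that structural equation modeling "will be used to test the conceptual models described in" section 4.4. The covariates for mother outcomes (4.4.1, 7.4.1) are site, use of other substances (at baseline, in 7.4.1) and intravenous route. None records adherence or illicit use between randomization and the blood sample. Section 7.8 has the time of the last dose recorded, but no analysis rule uses it.

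**The concern.** A mediator has to come before the outcome it is meant to explain. Here the first three or five weeks of the pregnancy outcomes come before the mediator.

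For adherence the reverse path is mechanical. Under 7.8 the BUP-SL trough is drawn before the first dose of the day and the BUP-XR trough just before the next injection. Doses missed in the preceding days or weeks therefore lower C_min, and the same missed days lower the adherence score. The two will correlate even if C_min has no influence on what the woman does afterwards.

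For illicit use the route is indirect. Illicit opioids do not set the buprenorphine level, but women who use early may also skip doses early.

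The secondary objective is to test the mechanism by which BUP-XR may work. If the full-pregnancy scores go into the model, a positive C_min-to-adherence path could not be told apart from early adherence producing C_min.

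**Working it through.** **The plan's own figure.** No power or effect size is given for the conceptual model. The only power statement is Table 8, for the primary non-inferiority test (margin 0.15, variance 0.11, one-sided 2.5%). Power = Φ(0.15/√(4×0.11/N) − 1.96).

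- N=176: √(0.44/176) = 0.0500, and Φ(3.00 − 1.96) = 85.1%, against 84.9% in the table.
- N=200: √(0.44/200) = 0.0469, and Φ(3.20 − 1.96) = 89.2%, against 89.0%.

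Table 8 reproduces, and this point does not touch it.

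**Overlap.** Entry is at 6 to 30 weeks EGA (6.4.2.1). Delivery at 40 weeks is the protocol's own example (4.2.1); 37 weeks is my assumption for a shorter case. The share of the pregnancy window before the sample is 3/(D − EGA) for week 3 and 5/(D − EGA) for week 5, where D is EGA at delivery.

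| EGA at entry | Window, D=40 | Before week 3 | Before week 5 |
|---|---|---|---|
| 6 | 34 weeks | 3/34 = 8.8% | 5/34 = 14.7% |
| 18 | 22 weeks | 3/22 = 13.6% | 5/22 = 22.7% |
| 24 | 16 weeks | 3/16 = 18.8% | 5/16 = 31.2% |
| 30 | 10 weeks | 3/10 = 30.0% | 5/10 = 50.0% |

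With D=37 the ranges are 9.7% (3/31) to 42.9% (3/7) for week 3 and 16.1% (5/31) to 71.4% (5/7) for week 5. If EGA at entry were uniform over 6 to 30 weeks with D=40 (assumption), the averages are 15% and 26%.

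**Illustrative simulation under the null.** C_min has no effect on anything later. The documents give no sub-study size, adherence distribution or adherence-to-C_min slope, so all of these are assumed: EGA uniform 6–30, delivery at 40 weeks, 35 early days of daily dosing, log C_min = log(0.3 + 0.9 × early adherence) + N(0, 0.35), and adherence propensities with logit mean 1.1 and SD 1. Early and late propensities are independent unless stated. The entries are rejection rates at nominal 5% for the C_min–adherence association.

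| Scoring | Women | Continuous C_min | C_min ≥ 1 ng/mL |
|---|---|---|---|
| From randomization | 100 | 38% | 23% |
| From randomization | 60 | 24% | 15% |

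Other assumed inputs gave higher rates from randomization:

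- Continuous C_min: 52% and 60% with 100 women, 35% and 39% with 60.
- Threshold: 30% with 100 women and 20% with 60.

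Scoring only after the sample gave 3.9% to 4.7% in these runs. For illicit use, one run (100 women, continuous C_min) gave 18.7% from randomization and 5.3% after the sample.

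**Is changing the window enough?** With an early–late correlation of 0.5 and 100 women, scoring after the sample alone still rejected in 61% (continuous) and 35% (threshold) of null runs. Adding pre-sample adherence as a covariate brought this back to about 5%.

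**The case against.** The strongest reply is that the plan does not say the model will use the full-pregnancy scores. Section 10.8 is one sentence, structural equation models can carry lagged paths, Figure 2a was not available, and section 10.4.2 announces a standalone SAP that was not available either. That stands as a limit on certainty. It does not remove the point: the pregnancy outcomes have one definition each, and an analyst following the available text would use it with nothing to correct the order.

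It can also be said that the plan does think prospectively. Section 4.4.1 justifies the week 3 sample by later dropout, and dropout feeds the outcomes: "If participants drop out of the study prematurely, they will be considered non-adherent for all days after drop-out", with missing urines imputed as positive (7.1.1). This is fair, but it leaves the pre-sample days inside the scores.

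Four stronger readings are tempting and are not supported:

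- That every outcome in the model overlaps the sample. Section 4.4.1 does not limit its outcomes to pregnancy, and the postpartum scores fall wholly after weeks 3 and 5.
- That illicit use itself produces the C_min value. The link runs only through skipped doses, and the simulated excess is much smaller.
- That a rate such as 60% belongs to this protocol. It comes from undocumented inputs and continuous C_min, whereas the main model uses the threshold. The simulation also gives every woman daily dosing, while women on weekly BUP-XR are credited seven days per staff-given injection.
- That moving the window repairs the analysis by itself. It does so only if early and late adherence are unrelated.

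**Conclusion.** The point holds for the pregnancy outcomes, chiefly adherence. As the available text stands, 15% to 50% of the pregnancy window precedes the week 5 sample and 9% to 30% precedes the week 3 sample (delivery at 40 weeks). A positive C_min-to-adherence path can then arise with no effect of C_min.

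The false-rejection rate for adherence is about 15% to 60% for 60 to 100 women if early and late adherence are independent, and higher if adherence tendency is stable. These rates show direction and rough scale only. A lag or adjustment in Figure 2a or the standalone SAP would settle the matter, and section 10.8 should then cite it.

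This concerns a secondary, mechanistic objective tested in an optional sub-study. The non-inferiority comparison and the other randomized comparisons are unaffected. The change should be made before the model is fitted.

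**What to change.** In 4.4.1 and 10.8, or in the SAP with a cross-reference:

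1. Score the mother model's pregnancy outcomes only from urines and dosing days after the C_min sample in use: after week 3 when the week 3 value is the mediator, after week 5 when the week 5 value is.
2. Enter adherence and urine results from randomization to that sample as covariates, or fit a cross-lagged structural equation model. This step is essential, because the window change alone leaves confounding by a stable adherence tendency.
3. Keep the randomization-to-delivery scores for the treatment comparison.

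No new data are needed: urines are collected weekly, and dispensing, injection and self-report records already exist. The cost is three to five fewer urines per woman in this analysis and some loss of precision. The analysis is also limited to women who were sampled and were still pregnant afterwards, and the report should state that restriction.

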3.2 Study Design

This is an intent-to-treat, two-arm, open-label, pragmatic randomized controlled trial. Eligible participants will be randomized in a 1:1 ratio to BUP-XR or BUP-SL, balancing on site, estimated gestational age (EGA) at time of randomization (6 weeks-18 weeks vs. 19 weeks-30 weeks), and whether they are on BUP-SL at the time of randomization (yes vs. no). Participants will be provided with study medication and attend weekly medication visits through 12 months postpartum. Participants will be invited to participate in the conceptual model assessment (CMA) sub-study, which will be used to evaluate the MOMs conceptual models. Infant caregivers will be invited to participate in the infant neurodevelopmental outcomes (INO) sub-study, which will include a 24-month child assessment. The INO data will be locked separately from the rest of the CTN-0080 database to allow CTN-0080 database lock following collection of the final (non-INO) CTN-0080 data point.

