4.1.3 Daily Peak-Trough Effects

In individuals with OUD, the daily BUP-SL trough is problematic in that plasma levels may be insufficient for suppressing opioid withdrawal symptoms.¹⁹ In pregnant women, both the BUP-SL peak and trough may be problematic. For the fetus, the BUP-SL peak is associated with adverse effects, including decreased fetal heart rate and heart rate variability.²⁴ Problems with BUP-SL trough are likely exacerbated in pregnant women, relative to non-pregnant individuals, since BUP is cleared more rapidly during pregnancy.^{25, 26} Research suggests that BUP plasma concentrations ≥ 1 ng/mL are required to suppress opioid withdrawal symptoms²⁷ and, thus, BUP-

SL should be dosed to maintain individuals at ≥ 1 ng/mL throughout the dosing cycle.¹⁹ Modeling studies suggest that plasma concentrations of 2-3 ng/mL are required for opioid blockade;^{19, 28} however, analysis of a recent opioid blockade study²⁹ revealed that BUP plasma concentrations ≥ 1.25 ng/mL were sufficient for achieving complete opioid blockade.³⁰ Thus, BUP plasma concentrations ≥ 1 ng/mL should, theoretically, be sufficient for suppressing opioid withdrawal and, for the subset of patients who use illicit opioids, BUP plasma concentrations ≥ 1.25 ng/mL should be sufficient to block illicit opioid effects. The results of a recent pharmacokinetic (PK) study indicate that pregnant women treated with BUP-SL may have BUP plasma concentrations < 1 ng/mL, and, thus, be at sub-therapeutic doses, for most of their dosing interval.³¹ Utilizing higher BUP-SL doses²⁶ and more frequent dosing in pregnant women³¹ have been recommended as potential solutions. However, higher doses may be problematic from the perspective of fetus-infant outcomes in that higher maternal BUP-SL doses may be associated with: 1) greater depression of fetal heart rate even at trough;²⁴ 2) lower birth weight and length;³² and 3) greater NAS/NOWS severity.^{32, 33} Using a more frequent dosing schedule may also be problematic in that greater than once daily dosing is associated with lower rates of medication adherence.^{34, 35}

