7.4.1 Covariates for Mother Outcomes

Two covariates will be controlled for in the mother outcomes in addition to study site: 1) the use of other substances at baseline, which can impact both treatment adherence and illicit opioid use and 2) route of illicit opioid use (intravenous vs. not intravenous); the Phase 3 CAM2038 trial found that illicit use outcomes were significantly better for CAM2038, relative to BUP-SL, for participants with intravenous use.⁵⁹

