2. Fetal Assessment at ~36 weeks EGA. The peak-trough effects for BUP-SL increase with increasing EGA²⁴ and, thus, the timing of this assessment will be at approximately 36 weeks EGA; this timing should increase the likelihood of observing BUP effects while helping to ensure that the majority of participants are still pregnant. The fetal assessment, consisting of a non-stress test (NST) and biophysical profile (BPP), will be obtained at approximately C_{max} , which is when the BUP effect on the fetus is most likely to be observed. For BUP-SL participants, the monitoring session will occur approximately 2.5 hours after dosing. For BUP-XR participants, the monitoring session will occur approximately 24 hours after injection.²⁹ The NST will use Doppler measurement to assess fetal heart function over a continuous observation period of ≥ 20 minutes.¹⁷² The BPP will use ultrasound imaging over a 30-minute period to determine a total score (range: 0-10) based on five parameters: 1) a reactive NST; 2) two or more gross body movements; 3) one or more episodes of limb or hand flexion and extension (muscle tone); 4) breathing movements lasting at least 20 seconds; and 5) a normal amniotic fluid volume index (5-24 cm for the 4 quadrant total).¹⁷² As noted in **section 4.4**, the variable of most interest is fetal heart rate variability (FHRV) at ~36 weeks EGA. Fetal heart rate accelerations, a measure of episodic FHRV,^{24, 69} will be used as the FHRV measure for MOMs. Jansson et al. recently reported that FHR accelerations at ~36 weeks EGA were significantly greater in number at BUP trough, relative to BUP peak.²⁴ In a secondary analysis of data from the MOTHER trial, Salisbury et al.¹⁷² reported significantly more FHR accelerations for women maintained on BUP-SL, relative to women maintained on methadone, at EGA ~32 weeks. Information about any action specifically taken as the result of the CMA fetal monitoring will be collected. While some sites may be equipped to perform this assessment in-clinic, it is likely that this assessment may occur at other clinical sites either within the institution or at an external clinical site providing these services.

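### The mother conceptual model lists no adjustment for BUP-SL status or EGA at randomization, so its trough-to-outcome path is open to confounding

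*Combined protocol and SAP*

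**What the plan says.** Section 4.4.1 sets out the mother model: treatment arm acts on the proportion of women with a trough of at least 1 ng/mL, which in turn is expected to reduce illicit use and improve adherence. On adjustment it says "Three covariates that are likely to impact mother outcomes will be controlled for in the analyses: 1) study site", followed by "2) use of other substances; and 3) route of administration of illicit opioid use (intravenous vs. not intravenous". BUP-SL dose and dosing frequency appear there only as ways to define subgroups.

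Section 7.4.1 gives the same set: "Two covariates will be controlled for in the mother outcomes in addition to study site". It words the substance-use item as "the use of other substances at baseline", a qualifier that 4.4.1 lacks.

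Section 10.8, the whole analysis section for this objective, says that structural equation modeling (SEM) "will be used to test the conceptual models described in" section 4.4. It names no terms.

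Randomization is balanced on site, EGA and BUP-SL status at randomization (3.2, 8.4). All three enter the primary model as random effects (10.3.2). Only site appears in the list for the mother conceptual model.

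**The concern.** Randomization protects the effect of arm on trough and the effect of arm on outcome. It does not protect the effect of trough on outcome, which is the mechanism claim. Trough varies between women within an arm, and anything that moves both trough and outcome will create or hide an association. A baseline variable that does so belongs in both equations.

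Two such candidates are stratification factors that the trial already records. If they are left out and matter, a significant trough path could be reported as support for the pharmacokinetic mechanism when it partly reflects who was newly starting treatment. Bias in the other direction, masking a real mechanism, is also possible.

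**Working it through.** **1. The plan's own figure.** The conceptual model has no stated power or sample size, so the only figure to reproduce is Table 8 (10.4.2). With variance 0.11 and margin 0.15, power = Φ(0.15/SE − 1.96), where SE = √(0.11 × 2/n per arm).
- N = 176: SE = √(0.11 × 2/88) = 0.0500; Φ(3.00 − 1.96) = 85.1% (stated 84.9%).
- N = 200: SE = √(0.11 × 2/100) = 0.0469; Φ(3.20 − 1.96) = 89.2% (stated 89.0%).

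The primary power reproduces, and this point does not touch it.

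**2. BUP-SL status: what the documents support.**
- *Trough side.* Section 4.4.1 estimates that BUP-XR reaches steady state at about study days 20-25. Week 3 is 3 × 7 = 21 days, inside that range, so the first sample is borderline for newly inducted women. Women already on BUP-SL move to a corresponding BUP-XR dose (9.3.1). Week 5 (day 35) is past the range.
- *Outcome side.* Section 4.4.1 says that dropout from BUP is concentrated in the first 30 days of treatment. Women not on BUP-SL enter that window at randomization; many established women may be past it. Missing urines count as positive (7.1.1, 10.3.5) and days after dropout count as non-adherent (7.2.1.1). Early dropout therefore feeds both outcomes through the scoring rules.

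**3. EGA: what the documents support.**
- *Trough side.* Section 4.1.3 says trough problems are probably worse in pregnancy "since BUP is cleared more rapidly during pregnancy", but that contrasts pregnant with non-pregnant people. Section 7.8 says "The peak-trough effects for BUP-SL increase with increasing EGA", but as the reason for timing the fetal assessment. Neither states that maternal trough falls as gestation advances.
- *Outcome side.* The number of expected urines depends on the time from randomization to delivery (10.3.2). With delivery at 40 weeks, the example in 4.2.1, entry at 6 weeks gives 40 − 6 = 34 urines and entry at 30 weeks gives 40 − 30 = 10. A woman who drops out after 4 negative urines scores 4/34 = 12% or 4/10 = 40%. EGA can thus shift the score without any difference in behavior.

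**4. Size if both links exist.** Simulation, 4,000 runs per cell, two-sided 5% test, no effect of trough on outcome.
- *From the plan:* mean 0.65, variance 0.11 (SD 0.332), 1:1 allocation.
- *Assumed:* sub-study size n; each factor binary, split evenly and coded s, e = ±1; correlation r of each factor with trough and with outcome; an arm shift of 0.5 SD in latent trough.
- *Latent trough:* C = rs − re + qz₁ + 0.5T, with q = √(1 − 2r²) and T the arm; C is dichotomized at its median.
- *Outcome:* Y = 0.65 + 0.332(rs − re + qz₂).
- *Fit:* Y on dichotomized trough and arm, then again with s and e added.

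The outcome gap between the two levels of a factor is 2 × r × 0.332.

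| r | Outcome gap per factor | Rejection without factors, n = 100 / 176 / 200 | Spurious path |
|---|---|---|---|
| 0 | 0 | 5.0 / 5.0 / 4.6% | 0 |
| 0.1 | 0.07 | 4.5 / 5.4 / 5.8% | about 0.01 |
| 0.2 | 0.13 | 9.7 / 13.8 / 14.3% | about 0.04 |
| 0.3 | 0.20 | 30.6 / 47.9 / 54.5% | about 0.10 |

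With both factors added, rejection is 4.4-5.3% in these cells and the mean path is about 0.

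Three limits apply. The fitted models omit the three covariates the plan does list. The two factors are simulated to bias the path in the same direction. The return to about 5% follows by construction, because no other confounder was simulated.

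**The case against.** The strongest reply is that silence is not exclusion. Section 4.4.1 is background and does not say that only these three covariates will be used. Section 10.8 lists no terms at all. Figure 2a is not visible in the text reviewed, and a standalone analysis plan mentioned in 10.4.2 could add terms. Section 10.3.2 treats the 7.4 covariates as additional to the randomization factors. All of this is fair, but the 10.3.2 sentence concerns the primary outcome, and nothing carries it into 10.8. What stands is that the text as written does not provide for the two factors.

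The second reply is that the associations are assumed. This stands. No section says directly that EGA or prior BUP-SL predicts illicit use. The steady-state argument rests on the BUP-XR half-life, so it is mainly a week-3 matter in that arm. Small associations do little: a 0.2 shift in log trough with a 5-point outcome gap gives rejection of 5.6% at n = 100 and 4.8% at n = 150.

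The third reply is that the fix does not make the path causal. This also stands. Dose in both arms can be adjusted for craving and withdrawal (9.1, 9.2), so it is a more direct common cause and would remain.

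A reader might infer from the missing baseline qualifier in 4.4.1 that on-study substance use will be adjusted for. Section 7.4.1 already gives the qualifier, so this is a matter of aligning two sections. A reader might also make much of the sub-study being voluntary. Loss of balance between arms is not the issue here: trough-outcome confounding arises even with perfect balance.

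**Conclusion.** The trough-to-outcome path is open to confounding by BUP-SL status at randomization and, on weaker grounds, by EGA. A reader might go further and conclude that the path is confounded and the mechanism estimate biased. The documents do not support that: they quantify neither association, and for EGA they give no gradient of maternal trough across gestation.

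The effect on a nominal 5% test runs from none (about 5-6% at r = 0.1) through modest (about 10-14% at 0.2) to serious (about 31-55% at 0.3). This depends on the assumed correlations, on a sub-study size of 100 to 200 that the documents do not state, and on a simplified model without the planned covariates. The consequence is confined to the mechanistic secondary objective; the primary and key secondary conclusions do not use this path. The change is worth making because it removes a plausible bias at almost no cost.

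**What to change.** In 4.4.1 and 10.8, state that EGA at randomization (continuous) and BUP-SL status at randomization (yes/no) enter both the trough equation and each outcome equation of the mother SEM, alongside the three covariates already listed. Word the substance-use covariate in 4.4.1 as in 7.4.1, so that it is clearly a baseline measure.

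Also state in 10.8 that the trough path will be reported as an association still subject to residual confounding between trough and outcome, for example through clinician-titrated dose. Add a sensitivity analysis showing how strong an unmeasured common cause would have to be to explain the path, for instance by varying the residual correlation between the trough and outcome equations.

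No new data are needed, since both factors are recorded at randomization. The cost is protocol or SAP wording and two more coefficients per equation: with one trough equation and two outcome equations, 2 × 3 = 6 parameters.
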